10.1.3.1. Handling/Storage/Accountability

The Eagle V1.2 Imaging System labels and labeling will be clearly identified by the Sponsor/Manufacturer as an investigational device. The PI and designees are responsible for maintaining control over the investigational device equipment maintained by the site. The investigational equipment must be segregated and provided only to participating investigators.

The following procedures will be followed to account for devices used in the clinical trial:

- All Handheld Fluorescence Cameras will be serialized
- The serial IDs of all serialized components of the Eagle V1.2 Imaging System will be recorded by the sites in the Device Accountability and Device Return/Repair/Destruction logs which will identify the storage location, date shipped, requested by, assigned to, date returned and include a record any issue(s) found with the system
 - o These logs must be stored in the same location as the Eagle V1.2 Imaging System
- Device serial numbers will be recorded on the Intraoperative Data Collection Tool at the beginning of each procedure
- All devices will be issued an RMA (return material authorization) number for return that will be listed on the packing slip when shipping. Details about cleaning before returning, should be documented in the Device Return/Repair/Destruction and communicated to the Sponsor prior to shipment.
- All devices will be shipped in a protected case
- The Eagle V1.2 Imaging System is to be used for the trial purpose only

Investigators will be responsible for maintaining all devices dedicated to the trial according to the study protocol and device manual/instructions for use to ensure optimal performance. The need

20-002 Rev:	A prospective multi-center clinical study evaluating the use of PD G 506 A and the Eagle V1.2 Imaging System for the visualization of carcinoma during breast conserving surgery	Page: 58 of 157
-------------	--	-----------------

for any non-routine maintenance will be reported by the investigator to the device manufacturer (SBI ALApharma Canada Inc.) as soon as the issue is observed. The device manufacturer will be responsible for performing and documenting any routine and non-routine device maintenance.

10.2. Method of Treatment Assignment

All participants will be centrally assigned to randomized study treatment using an Interactive Voice/Web Response System (IVRS/IWRS). Before the study is initiated, the telephone number and call-in directions for the IVRS and/or the log in information & directions for the IWRS will be provided to each site. Study treatment will be dispensed at the Day 1 study visit as summarized in the Schedule of Activities. Unused dispensed reconstituted investigational drug should be disposed of and should not be re-dispensed to another participant. The IVRS/IWRS will be used for both Part A and Part B as the first step for enrollment of a participant; all subjects in Part A will receive PD G 506 A and in Part B subjects will be randomized to receive PD G 506 A or placebo.

10.3. Blinding

Part A of the study is not blinded as all participants will receive PD G 506 A. Although surgeons will not be blinded to treatment in Part A, they will follow all of the same procedures as in Part B and will not perform any fluorescence assessments until SoC resection is complete. In the main study, Part B, the participants and pathologist(s) (and pathologist's assistant) will be blinded to the treatment assignment for the duration of the trial. The *surgeon* and *surgeon's assistant* will be blinded to the treatment assignment up until the time that the SoC lumpectomy procedure is complete, at which point they will be unblinded. The *surgeon* will also be blinded to the fluorescence imaging data collected by the *surgeon's assistant* during SoC (e.g. imaging data of the, *primary specimen* and *SoC-driven cavity shaves*) until such time that they are intentionally unblinded per protocol.

At clinical sites where specimen biopsies are collected from inside the sectioned specimen, the individual grossing the specimen (e.g. pathologist's assistant) will remain blind to the fluorescence imaging data collected by the *surgeon* or *surgeon's assistant*.

In order to maintain this blind, an otherwise uninvolved 3rd party (e.g. pharmacist) will be responsible for the reconstitution and dispensation of the study drug and dispensation of the placebo (drinking water) and will endeavor to ensure that there are no differences in time taken to dispense following randomization. The investigational drug or placebo will be administered by a blinded qualified medical professional (e.g. nurse). Neither the *surgeon* nor *surgeon's assistant* can administer the study drug due to the potential risk that the patient's reaction to consuming the investigational product accidentally unblinds the individual dosing them.

The sponsor must be notified before the blind is broken unless identification of the study treatment is required for a medical emergency in which the knowledge of the specific blinded study treatment

SBI-CIP 20-002 Rev: v1.8 A prospective multi-center clinical study evaluating the use of PD G 506 A and the Eagle V1.2 Imaging System for the visualization of carcinoma during breast conserving surgery Page: 59 of 157	
--	--

will affect the immediate management of the participant's condition. In this case, the investigator must notify the Sponsor's pharmacovigilance vendor, spmd (spmd will notify the Sponsor) within 24 hours after breaking the blind. The date and reason that the blind was broken must be recorded in the source documentation and electronic case report form (eCRF), as applicable.

For participants that are withdrawn or are terminated, the investigator may be unblinded to the treatment allocation following documentation of the participants withdrawal/termination.

If any member of the blinded research team (e.g. *surgeon*, *surgeon's assistant*, research nurse or pathologist) is inadvertently unblinded at any time other than as defined by the study protocol, data collection will continue as per protocol. The time that the blind was broken and individual that was unblinded will be noted in the eCRF.

In the event of a Quality Assurance audit, the auditor(s) will be allowed access to unblinded study treatment records at the site(s) to verify that randomization/dispensing has been done accurately.

10.4. Treatment Compliance

To minimize the risk of a phototoxic skin reaction all participants will be required to comply with written sun/light protection instructions provided by the Sponsor (SBI ALApharma Canada Inc.). See Appendix 3 for more details.

10.5. Concomitant Therapy

Any medication for concomitant diseases of the patient will be allowed during the course of the clinical study.

Participants will be provided with sunscreen to apply prior to leaving the hospital and for a minimum of 48 hours after administration of investigational drug when exposed to sunlight.

10.6. Prophylactic Medications, Treatments and Procedures

The participant may be administered antiemetics to mitigate the side effects of PD G 506 A, as medically required.

Participants will be advised to keep out of direct sunlight for at least 48 hours and given a small bottle of sunscreen (minimum sun protection factor (SPF) 60) as further prevention against photosensitization. Sunscreen will be self-administered by participants. While in the hospital and when possible, participants will be exposed to low light environment conditions (e.g. inpatient room will be turned off) following administration of the investigational drug.

10.7. Warnings and Precautions

Reduce direct exposure to sunlight or room lights for at least 48 hours after oral administration of the investigational drug.

SBI-CIP 20-002 Rev: v1.8 A prospective multi-center clinical study evaluating the use of PD G 506 A and the Eagle V1.2 Imaging System for the visualization of carcinoma during breast conserving surgery	Page: 60 of 157
---	-----------------

10.8. Prohibited Medications, Treatments and Procedures

Patients taking PD G 506 A who are exposed to a photosensitizing agent may experience a phototoxic skin reaction. Due to the risk of possible phototoxic reactions, study participants should avoid administering phototoxic drugs such as St. John's Wort, griseofulvin, thiazide diuretics, sulfonylureas, phenothiazines, sulphonamides, quinolones, and tetracyclines, and topical preparations containing ALA for 24 hours before and after administration of investigational drug.

Information regarding use of prohibited medications, treatments and procedures will be collected during screening and at all study visits. Treatment with any the above listed medications will not be permitted unless discussed with and approved by the investigator and Sponsor. If treatment with any of the above listed medications is commenced prior to administration of the study drug, the participant will be terminated early. If treatment with any of the above listed medications is commenced following administration with study drug, early termination will require discussion and approval by the investigator and sponsor.

11. Termination of Participation/Withdrawal Criteria

The following criteria apply to participants who have been enrolled in the study. An enrolled participant will be automatically withdrawn from the study if their surgery is re-scheduled at a site other than a study site or if their treatment plan is modified such that they no longer meet the study eligibility criteria. A participant may verbally withdraw at any time by contacting her surgeon or appropriate study staff (e.g. study coordinator).

An investigator may terminate a patient's participation in the study if: any clinical AE, laboratory abnormality, or other medical condition or situation occurs such that continued participation in the study would not be in the best interest of the participant.

Reasons for withdrawal or termination will be recorded in the participant's study record.

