11.1. Handling of Participant Withdrawals or Termination

All data collection relating to a withdrawn or terminated participant, excluding safety data for participants that have received PD G 506 A, will cease at the time of withdrawal/termination. Clinical care in all withdrawn or terminated participants will continue as per standard of care.

In order to maintain the required number of study subjects, any participant that withdraws or is terminated prior to completion of the Week 2 visit will be replaced. Participants that withdraw or are terminated after the Week 2 visit but prior to the 1 year follow-up will not be replaced.

SBI-CIP 20-002 Rev: v1.8 A prospective multi-center clinical study evaluating the use of PD G 506 A and the Eagle V1.2 Imaging System for the visualization of carcinoma during breast conserving surgery	Page: 61 of 157
---	-----------------

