12.7. Week 2 Visit (Day 10 – 14)

Clinical usefulness and diagnostic performance endpoint data will be collected at the participant's post-operative surgical follow-up visit.

At this visit, the participant will complete the post-operative Breast Conserving Therapy Module of the Breast-Q survey. To minimize the potential impact of timing of administration of the Breast-Q survey post-op questionnaire, all patients will complete the 2-week post-op questionnaire before they have met with their *surgeon* to discuss their surgical pathology report.

The participant's surgical pathology report will be available at this time. Endpoint data will be retrieved from the participant's surgical pathology report and the study-specific Pathology Data Collection Tool. Additional data related to the final pathological tumor staging, pathological features/characteristics and nodal involvement will be retrieved from the participant's surgical pathology report and recorded in the eCRF.

The *surgeon* will question the patient about any patient-reported Aes and use of concomitant medications as well as assess and record any ongoing adverse events in the participant's medical record and eCRF.

Blood work (CBC, AST, ALT, TBL, creatinine) will be performed at this visit. If liver enzymes are elevated from baseline (and deemed clinically significant according to the **Table 12.2** below), the patient will be followed until such time that liver enzyme levels return to baseline. Physical examination must include assessment of any phototoxicity reactions and any observed phototoxicity reactions will be followed until resolution.

Table 12.2: Criteria for clinical significant liver enzyme elevation

	SBI-CIP 20-002	Rev: v1.8	A prospective multi-center clinical study evaluating the use of PD G 506 A and the Eagle V1.2 Imaging System for the visualization of carcinoma during breast conserving surgery	Page: 77 of 157
--	-----------------------	--------------	--	-----------------

Criteria	CTCAE v5.0 Grade 2 (moderate) as criterium to judge if elevation of liver enzymes should be deemed clinically significant
Bilirubin: above upper limit of normal	Bilirubin:
	> 1.5 – 3.0x institutional* ULN if baseline normal
	> 1.5 – 3.0x baseline if baseline abnormal
AST: > 2.5x institutional ULN	AST:
	> 3.0 – 5.0x institutional* ULN if baseline normal
	> 3.0 – 5.0x baseline if baseline abnormal
ALT: > 2.5x institutional ULN	ALT:
	> 3.0 – 5.0x institutional* ULN if baseline normal

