12.10. Early Termination Visit

If early termination occurs prior to administration of the investigational drug (and use of the Eagle V1.2 Imaging System) no additional study specific procedures or evaluations are required and no early termination visit is required. If early termination occurs following administration of the investigational drug (e.g. during the surgery the *surgeon* decides it is not in the best interest of the patient to proceed with the study specific data collection), safety data including AEs and medical device problems will be collected and recorded on the procedure day (Day 1). The participant will continue to be followed for AEs until the Week 2 Visit. No specific early termination visit is required.

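### Termination between surgery and Week 2 stops pathology collection and triggers replacement, so an operated and imaged Arm 2 patient can leave the primary analysis on a discretionary decision

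*Combined protocol and SAP*

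**What the plan says.** **Who can be terminated after dosing.**
- Section 10.8 does not make termination automatic for a listed drug started after dosing. If it is "commenced following administration with study drug, early termination will require discussion and approval by the investigator and sponsor". The same section asks patients to avoid these drugs "for 24 hours before and after administration of investigational drug", and says that information on their use "will be collected during screening and at all study visits".
- Section 11 lets the investigator terminate for an adverse event, laboratory abnormality or other situation in which "continued participation in the study would not be in the best interest of the participant". There is no cut-off at surgery.
- Section 12.10 gives as an example of termination after dosing that "during the surgery the *surgeon* decides it is not in the best interest of the patient to proceed with the study specific data collection". It then names only safety data for collection.

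**What follows from termination.** Under section 11.1, data collection, "excluding safety data for participants that have received PD G 506 A, will cease at the time of withdrawal/termination". Also, "any participant that withdraws or is terminated prior to completion of the Week 2 visit will be replaced". Patients who leave after Week 2 are not replaced.

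**When the endpoint is captured.** Section 12.7: "Clinical usefulness and diagnostic performance endpoint data will be collected at the participant's post-operative surgical follow-up visit". The surgical pathology report is available by that visit.

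**Who is analysed.** Section 15.4.1 defines the mITT for Arm 2 as randomized, dosed, imaged and with recorded surgical pathology. It adds that missing data will be imputed and leaves the method to the SAP. Section 15.2 and the synopsis describe the mITT as Arm 2 patients who have surgery and recorded histopathology, without naming imaging.

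**The concern.** The primary endpoint is fixed by tissue removed on Day 1. Nothing that happens afterwards can alter it, so there is no scientific reason for a later termination to cost the trial that observation. Yet sections 11.1, 12.7 and 15.4.1 together allow this in the days between surgery and the recording of pathology.

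By then the surgeon has been unblinded (section 10.3) and has assigned a fluorescence status to every imaged surface (section 12.4.3). Some reasons for stopping, such as an adverse event after more tissue was taken, may be related to fluorescence-guided resection (FGR) itself. P(1.1) is a single-arm proportion tested against 1%, so a control arm cannot offset selection into the denominator. P(2.1), P(2.2) and P(2.3) use the same population.

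The plan protects data in comparable situations. Section 11.2 keeps data through Month 3 for patients lost in the extension phase, and section 10.3 continues collection after accidental unblinding. No matching sentence covers the time between surgery and Week 2.

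**Working it through.** **1. The route, step by step, for an Arm 2 patient**

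| Stage | Section | Consequence |
|---|---|---|
| Dosed, resected, imaged, fluorescence status recorded | 12.4.3 | Surgeon knows arm and fluorescence result |
| Terminated by judgement before Week 2 | 10.8, 11, 12.10 | No exception for operated patients |
| Non-safety collection stops | 11.1 | Pathology not yet recorded need not be retrieved |
| Recorded pathology required | 15.2, 15.4.1 | Not in the mITT, unless the imputation sentence is meant to cover her |
| Replaced | 11.1 | Another patient takes her place |

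If her pathology is already recorded, she stays in the mITT and is still replaced. That does not select the denominator, but the replacement rule then serves no purpose.

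**2. Reproducing the plan's sample size**

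Inputs (section 15.2): null p0 = 0.01, expected p1 = 0.03, two-sided alpha 0.05, power 90%, allocation 1:6, 5% loss.

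n = [(1.960 × √(0.01 × 0.99) + 1.2816 × √(0.03 × 0.97)) / 0.02]² = 427.7, so **428**, the stated Arm 2 figure. Then 428 × 7/6 = 499.3, so 500, and 500 × 1.05 = 525, also as stated.

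**3. The decision rule**

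Section 15.6.1 requires the Wilson 95% lower bound to exceed 1%. At n = 428, 8 conversions give 0.950% (fail) and 9 give 1.110% (pass). With at least 9 of 428, exact power at 3% is 89.6% and exact one-sided type I error at 1% is 3.0%. That 3.0% is the baseline before any selection.

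**4. Selective removal of non-converters, with replacement**

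The documents give no termination frequency, so the share f of non-converters removed is assumed. The analysed number stays at 428 and the conversion proportion among those analysed becomes p′ = p / [p + (1 − p)(1 − f)]. At a true p of 1%, the number removed to end with 428 analysed is 428 / [0.01 + 0.99(1 − f)] − 428.

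| f (assumed) | Removed, about | p′ | Type I error |
|---|---|---|---|
| 0 | 0 | 1.00% | 3.0% |
| 1% | 4 | 1.01% | 3.2% |
| 2% | 9 | 1.02% | 3.4% |
| 5% | 22 | 1.05% | 4.0% |
| 10% | 47 | 1.11% | 5.2% |

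**5. Loss of converters, with replacement**

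About 428 × 0.03 = 12.8 conversions are expected. If a share g (assumed) is lost, p′ = 0.03(1 − g) / (1 − 0.03g).

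| g (assumed) | Conversions lost (12.8 × g) | p′ | Power |
|---|---|---|---|
| 0 | 0 | 3.00% | 89.6% |
| 5% | 0.6 | 2.85% | 86.2% |
| 10% | 1.3 | 2.71% | 82.0% |
| 20% | 2.6 | 2.41% | 70.7% |

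Per patient, losing a converter matters far more than losing a non-converter, so the rule can also hurt a drug that works.

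**The case against.** The strongest reply is that the rule is narrower than it looks, and much of that reply stands.

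- **A reader might infer that termination after surgery erases the margin pathology.** It does not. Section 11.1 stops collection from that time on; nothing deletes recorded data. Fluorescence status is recorded on Day 1, the pathologist records margins under section 12.6 without a visit, and the mITT has no exclusion for termination as such. The route is open only until pathology is recorded.
- **A reader might infer that an antibiotic several days after surgery removes the patient.** The listed drugs are restricted for 24 hours either side of dosing, and termination needs discussion and approval. The closing sentence of section 10.8 does not repeat the window, so the two should be reconciled, but a late prescription is not shown to be a ground for removal.
- **A reader might infer that the decision is wholly unblinded.** Unblinding is documented for the surgeon and surgeon's assistant. The documents do not say what the sponsor's decision-makers know.
- **A reader might infer that patients whose FGR is abandoned escape the denominator.** Where imaging was done, they do not escape merely because resection stopped. Section 5.2 counts such a patient as having undergone FGR, section 12.4.3 records residual fluorescence and the reason for stopping, and section 15.6.1 does not let those orientations count towards a negative final margin. Patients never imaged lie outside the endpoint's own denominator (section 7.1), so they should not be added to it.
- **A reader might subtract the 5% loss from 428 and find that 8/406 passes (1.002%) where 8/428 fails.** The 5% is already in the 525, which gives 525 × 6/7 = 450 in Arm 2. Removing 22 from 450 returns 428, and 9 conversions are needed at both sizes (8/450 gives 0.904%, 9/450 gives 1.056%). That scenario also ignores replacement.

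The imputation sentence in section 15.4.1 might be meant to cover these patients. It is not reconciled with a population that requires recorded pathology, and it would be odd to impute a result that the hospital's pathology report already contains.

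What remains is the rule itself: collection stops and replacement follows, with no exception for a patient whose endpoint tissue has already been taken.

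**Conclusion.** The point holds in this limited form. Between surgery and the recording of pathology, a discretionary termination can take a dosed, imaged and resected Arm 2 patient out of P(1.1) and P(2.1) to P(2.3) and bring in a replacement, after the surgeon knows the arm and fluorescence status.

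The numerical effect is modest. Type I error at a true 1% moves from 3.0% to between 3.2% and 5.2% for an assumed 1% to 10% of non-converters selectively removed. Power falls from 89.6% to 86.2% or 82.0% if 5% or 10% of converters are lost. These figures rest on assumed shares and on selection that depends on the outcome; the documents give no evidence of either. The case for change is that the route has no purpose and is cheap to close, not that the planned analysis is invalid. Whether use of a listed drug should lead to termination is a clinical rule and is not judged here.

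**What to change.** This concerns data handling only.

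1. In sections 11.1 and 12.10, add:

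> For every Arm 2 participant who has been dosed and imaged, the recorded fluorescence data and all pathology from the index surgery are collected and analysed in the mITT regardless of later withdrawal or termination, unless consent to use the data is withdrawn.

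2. In section 11.1, limit replacement to participants who leave before surgery.
3. Reconcile the mITT wording in section 15.2 and the synopsis with section 15.4.1: whether imaging is required, and how imputation fits with a requirement for recorded pathology.
4. Reconcile the 24-hour window in section 10.8 with its closing sentence on termination, which has no end date. The clinical content is for the sponsor and investigators.

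**Cost.** Amendment text only. The pathologist already reports final margin status in the medical record (section 12.6.1), and the Arm 2 requirement stays at 428. The observed conversion rate may be slightly lower than under selective removal, and fewer patients will be replaced.
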